Analysis Plan: Patient Centered Support for Contraceptive Decision-Making: A Cluster Randomized Controlled Trial of a Contraceptive Decision-Support Tool

Principal Investigator: [name] MAS

Intention-to-treat analysis

Participants who “cross over” from their assigned study arm (as determined by the provider they are likely to see) will be included in the final analyses in the arm in which they were initially assigned.

Modified intention-to-treat analysis: Post-randomization exclusion

Some participants may be excluded from analysis after being randomized:

- Participants who find out they are pregnant during their enrollment visit (and thus would have been ineligible had this been known prior to enrollment).
- Participants who enrolled in the study more than once (their second enrollment will be excluded).

Data Collection and Analysis

The outcomes of interest for this study have been divided into three specific aims, which dictate what type of data is collected and how it is analyzed.

Outcomes of Interest

Specific Aim 1: The primary outcome is a binary indicator of contraceptive continuation at 7 months and a secondary outcome is a binary indicator of contraceptive continuation at 4 months. For ambiguous cases for these outcomes, we used a blinded adjudication process and applied a standardized list of rules and assigned outcomes throughout the process of data collection. Potential outcomes for individuals are as follows: continuous users of chosen method, non-continuous users of chosen method, and missing but included and imputed.

For all variables, the analysis will use multiple imputation to deal validly with the missing values. Of note, specific variables were not collected from participants we collected data from more than 48 hours after their visit. Those variables will be analyzed in the same way as other missing outcomes.

- **Primary outcome:**

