 - Continuation of the chosen method seven months after her visit, without a gap of four consecutive weeks or more. If participants completed a 4 month follow-up survey, they must have started their chosen method by the date of that survey to be considered continuous users. If they did not complete a 4-month follow-up survey and only completed a 7-month follow-up survey, they must have started their chosen method by 20 weeks post-enrollment (4 weeks after their 4-month follow-up milestone). Participants must be currently using their chosen method at the time of the 4-month follow-up survey to be considered continuous users, UNLESS they report this non-use as

part of a <4week gap at the time of the 7 month survey. Participants must be currently using their chosen method at the time of the 7-month follow-up survey to be considered continuous users.

- *Definition of continuation variable:* We will evaluate continuation based on the day of 7-month survey completion, within a 4-week window beginning 7 months after enrollment
- *Definition of chosen method:* In the primary analysis, continued use of any IUD among those choosing either IUD will be classified as continued use of the chosen method; we will conduct an additional sensitivity analysis in which only continued use of the type of IUD originally chosen will be classified as continuous.
- *Treatment of bridge method users:* For primary analysis, any combination of continuous bridge method use with or without subsequent use of the chosen method will be considered continuous; we will conduct a sensitivity analysis in which participants who never start their primary OR start their primary method after the 4-month follow-up survey are not considered continuous users of their chosen method.
- *Treatment of women who become pregnant.* Continuation at 7 months will be multiply imputed for participants who report a pregnancy before this point who had started their chosen method before 4 months and were continuing to use it at the time they became pregnant. Participants reporting discontinuation prior to pregnancy will be counted as non-continuers.
- *Continuous users of coitally-dependent methods:* For primary analysis, in addition to the standard definition of who is a continuous user of a chosen method, choosers of coitally-dependent methods will also be categorized as continuous users if they:

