 - Continuation of the chosen method four months after enrollment, without a gap of four consecutive weeks or more. In order to be considered continuous users. If participants completed a 4-month follow-up survey, they must have started their chosen method by the date that survey to be considered continuous users. If they did not complete a 4-month follow-up survey and only

completed a 7-month follow-up survey, they must have started their chosen method by 20 weeks post-enrollment (4 weeks after 4-month follow-up milestone). Participants must be currently using their chosen method at the time of the 4-month follow-up survey to be considered continuous users, UNLESS they report this non-use as part of a <4week gap at the time of the 7-month survey.

- *Definition of continuation variable:* We will evaluate continuation based on the day of 4-month survey completion, within a 4-week window beginning 4 months after enrollment
- *Definition of chosen method:* For primary analysis, we will collapse IUD types for chosen method; we will conduct an additional sensitivity analysis in which we do not collapse IUD types
- *Treatment of bridge method users:* For primary analysis, any combination of continuous bridge method use with or without subsequent use of the chosen method will be considered continuous; we will conduct a sensitivity analysis in which participants who never start their primary OR start their primary method after 4mo follow-up survey are not considered continuous users of their chosen method
- *Treatment of women who become pregnant.* Continuation at 4 months will be multiply imputed for participants reporting a pregnancy before this point who had started their method and continued to use it until they became pregnant and for those who never started their method before their 4 month survey. Participants reporting starting and then discontinuing their chosen method prior to pregnancy will be counted as non-continuers.
- *Continuous users of coitally-dependent methods:* For primary analysis, in addition to the standard definition of who is a continuous user of a chosen method, choosers of coitally-dependent methods will also be categorized as continuous users if they:
 - 1) Did not have a gap of 4+ weeks during which they were sexually active and did not use a Tier 1 or Tier 2 method at any point since enrollment for four weeks or more (asked about a gap when were sexually active in the gap question) OR

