 - 2) Report that they discontinued the method at the time of their survey BUT are not using anything else, have not had sex since discontinuation and say they would use this method if they were to have sex (note: no participants met this criteria) OR
 - 3) Never started the method but haven't had sex since enrollment and would use the method if they started having sex (note: no participants met this criteria)

Pre-specified covariates for patients for Specific Aim 1:

- Age
 - <20
 - 20-24
 - 25-29
 - 30-34
 - ≥35
- Parity
 - 0
 - ≥1
- Race/ethnicity
 - White
 - Black
 - Latina
 - Other
- Language
 - English
 - Spanish
- Parental education
 - ≤ High school
 - Some college
 - ≥ College

Pre-specified covariates for providers for Specific Aim 1:

- Age
 - <36
 - 36-50
 - ≥51
- Race/ethnicity
 - White
 - Other
- Professional Degree
 - NP
 - Non-NP

Specific Aim 2: Qualitative assessment of patient engagement and the presence of shared decision making between counseling provided before and after implementation of the decision support tool by providers randomized to the intervention group. As described above, the qualitative coding will focus on the presence or absence of shared patient-provider decision making and patient engagement in the decision making process, drawing on concepts from observational measures of shared decision making, as well as insights into the counseling process gained through our previous observational study.

Specific Aim 3:

- Qualitative assessment of providers' and staff members' experiences using interviews and focus groups
- Quantitative measures of consultation time and total clinic visit time
 - Total Clinic Visit Time
 - Total amount of time a patient spends in a clinic for a family planning visit, from check-in to check-out.
 - Time of visit end minus time of check-in (recorded in clinic tracking sheets)
 - Time Spent with Contraceptive Counseling Provider
 - Total amount of time spent with the provider that is providing contraceptive counseling.
 - Time of visit start minus time of visit end (recorded in clinic tracking sheets)
 - **Note:** this measurement will be different at PP Valencia because consultation time included time spent with RHS and clinician, rather than a singular contraceptive counseling provider as at other clinics
- Change in provider burnout, pre- and post-intervention, using the Maslach Burnout scale, measured prior to implementation of the intervention and at the end of the trial

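### The 4-month continuation outcome imputes pregnant women who never started their method, although its own start requirement already settles their status and the 7-month primary outcome does not impute them

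*SAP*

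**What the plan says.** All rules below are in the SAP, under Outcomes of Interest, Specific Aim 1.

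**4-month continuation (secondary outcome).**
- Start requirement for women who completed the 4-month survey: "they must have started their chosen method by the date that survey to be considered continuous users".
- Pregnancy clause: imputation covers women who used their method until they conceived, "and for those who never started their method before their 4 month survey".
- The same clause fixes one group as failures: "Participants reporting starting and then discontinuing their chosen method prior to pregnancy will be counted as non-continuers".
- Bridge users are an exception to the start requirement: "any combination of continuous bridge method use with or without subsequent use of the chosen method will be considered continuous". A planned sensitivity analysis reverses this for those who never start the main method or start it late.
- One coitally-dependent rule is written for never-starters. It requires no sex since enrollment and that the woman "would use the method if they started having sex (note: no participants met this criteria".

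**7-month continuation (primary outcome).**
- The start requirement is tied to the same survey: "they must have started their chosen method by the date of that survey to be considered continuous users".
- Imputation after pregnancy is limited to women "who had started their chosen method before 4 months and were continuing to use it at the time they became pregnant".

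For ambiguous cases, the SAP says that "we used a blinded adjudication process and applied a standardized list of rules". The rule list itself is not in the documents.

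**The concern.** Imputation is for outcomes that are not known. The start requirement makes the 4-month status of a surveyed never-starter known, yet becoming pregnant moves her back to unknown. She can then be drawn as a continuer of a method she never used, while a pregnant woman who used her method and stopped cannot. The primary outcome applies the same deadline and does not reopen her status.

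What is at stake is the meaning of the 4-month outcome and its agreement with the 7-month one. The two are meant to measure the same thing at successive times, and here they treat one fact at one date differently without explanation.

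**Working it through.** **Step 1. The rules side by side.** The table takes women who completed the 4-month survey, with pregnancies before month 4, and sets the bridge and coitally-dependent rules aside.

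| Situation | 4-month outcome | 7-month outcome |
|---|---|---|
| Not pregnant, never started by the survey | Non-continuer | Non-continuer |
| Pregnant, started, using at conception | Imputed | Imputed |
| Pregnant, started, stopped before conception | Non-continuer | Non-continuer |
| Pregnant, never started by the survey | **Imputed** | **Non-continuer** |

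Only the last row differs. The 7-month pregnancy clause does not name this woman; the start requirement settles her status there. The bridge rule does not explain the difference, because the 4-month clause is not restricted to bridge users. Nor does the coitally-dependent rule for never-starters: it requires no sex since enrollment, which hardly fits a woman who conceived after enrolling, and the SAP notes that nobody met it.

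**Step 2. How many women.** The plan gives no count, so this is an illustration.

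Inputs from the protocol's Sample Size section: 758 patients, 20% loss, 50% and 62% continuation at 7 months, 5% unintended pregnancy (no period stated).

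Assumptions: the 5% is a 7-month figure accruing evenly; 20% to 50% of women pregnant by month 4 had never started; none is a bridge user.

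- Pregnant by month 4: 758 × 0.05 × 4/7 = 21.7. After loss: 606.4 × 0.05 × 4/7 = 17.3.
- Never started: 21.7 × 0.20 to 0.50 = 4.3 to 10.8. After loss: 3.5 to 8.7.

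**Step 3. Shift in the between-arm difference if the clause is removed.** Removing it turns draws at the imputed rate into zeros, so the intervention-minus-control difference moves by

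s × (c × pc − t × pt),

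where s is the never-started share, c and t are the pregnancy rates by month 4 (control, intervention), and pc and pt are the imputed continuation rates. Women negative at 4 months are carried forward as negative at 7 (SAP, Methods of Analysis), so 4-month rates should be at least the 7-month ones. I use 50/62% to 70/82%. The even-accrual rate is 5% × 4/7 = 2.86%.

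| Pregnancy rates (control, intervention) | Shift, percentage points |
|---|---|
| 2.86%, 2.86% | −0.07 to −0.17 |
| 2.86%, 1.43% | +0.11 to +0.41 |
| 1.43%, 2.86% | −0.21 to −0.67 |

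For example, the largest is 0.50 × (1.43 × 0.70 − 2.86 × 0.82) = −0.67. If the higher arm's rate is 2% and the other arm's is half that, the extremes are −0.47 and +0.29; with 5% they are −1.18 and +0.73.

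**Step 4. Against sampling error.** SE = √[pc(1−pc)/n + pt(1−pt)/n], ignoring clustering.

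- n = 379 per arm: 3.58 points (50/62%) and 3.07 points (70/82%).
- n = 303 per arm: 4.00 and 3.44 points.

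Largest main-scenario ratio: 0.67/3.07 = 0.22, or 0.67/3.44 = 0.19 after loss. With all 5% pregnant by month 4, it is 1.18/3.07 = 0.38.

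**Step 5. Dependence on the imputation model.** The Missing data paragraph does not list the predictors. If start status is one, never-starters outside bridge use are drawn near zero and the shift is about 0.

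**The case against.** The strongest reply is that the clause is explicit and may be deliberate. It names pregnant never-starters and says what to do with them, and a specific rule overriding a general one is ordinary drafting. A woman may start as late as her 4-month survey date, so a pregnancy before then cuts off a status that was still open. One who started and stopped had already failed. Treating the first as missing and the second as observed is coherent. The 7-month clause must also cover pregnancies after month 4, when the start deadline has usually passed, so a narrower group is natural there.

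Much of this stands. An analyst can follow the clause, and the 7-month rule does not by itself make the 4-month rule wrong, because it governs a different outcome. But for a pregnancy before month 4, the lost chance to start is the same at both time points, and only one definition allows for it. The clause also covers a woman who left the method unstarted for months before conceiving. No reason for either choice is written. That argument could equally support widening the 7-month rule, but doing so would change the primary outcome after outcome data had been seen.

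Existing safeguards help only in part. The bridge sensitivity analysis sits under the bridge heading, and its interaction with the pregnancy clause is not stated. The informative-missingness analysis lowers imputed continuation for everyone with a missing outcome and does not isolate these women. Record review of every pregnancy is planned, but the written clause still sends them to imputation.

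**Conclusion.** The inconsistency holds and is minor. It lies within the 4-month entry; the 7-month entry supports it by using the same deadline with a narrower imputed group. The size rests on an assumed pregnancy period, never-started share and arm difference, and on an imputation model that the SAP does not specify.

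A reader might infer that the primary result is compromised, that the trial loses power, or that the clause favours the intervention. The documents support none of these. The clause defines the 4-month outcome only, the affected group is probably a handful of women, and the sign of the shift depends on which arm has more such pregnancies, which is unknown. Nor do the documents show that the clause was a drafting error; they show only that it is unexplained and does not match the primary rule.

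**What to change.** Edit the 4-month pregnancy clause to match the primary rule: impute only pregnant women who had started and were using the method at conception. Score surveyed pregnant never-starters as non-continuers, with two exceptions. Women in continuous bridge use up to the pregnancy are still imputed, and the existing bridge sensitivity analysis covers them. Women who meet a coitally-dependent rule keep that classification.

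Leave the 7-month primary definition unchanged. Bridge users who conceive without starting will then still be described differently at the two time points, but removing that difference would mean altering the primary outcome.

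The SAP's notes that no participant met certain criteria show that some outcome data had been reviewed. The change should therefore be dated and disclosed, and the 4-month result under the current clause reported as a sensitivity analysis.

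If the sponsor prefers to keep the exception, report the 4-month result with these women as non-continuers as the sensitivity analysis, and state why the exception does not apply at 7 months.

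The cost is one edited clause, a dated note and one rerun of the 4-month analysis. No new data are needed, since record review of all pregnancies is already planned.

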- The recordings from these visits will be transcribed on a computer by a HIPAA-compliant transcription service.

Study Protocol

Patient Centered Support for Contraceptive Decision-Making: A Cluster Randomized Controlled Trial of a Contraceptive Decision-Support Tool

November 22, 2016

- After completing three visits, each provider will complete a survey about their demographic characteristics and the Maslach Burnout Inventory.

The procedure for patient participants is as follows:

- After being screened and consented by study staff, each patient will complete a short demographic survey (**Note:** This survey was not added to study procedures until 11/4/15, when a minor modification detailing it was approved) and have a family planning visit in the usual fashion as is performed at the clinic with providers participating in the study. As described above, the conversation between patient and provider will be recorded on a secure voice recorder during these visits, and the visits will be transcribed.

2. Randomization

After the pre-intervention phase and before the intervention phase, the provider participants will be randomized into intervention and control arms, stratified by clinic. Providers will be randomized using a random number table, clustered by each clinic. [name] will create a random number table using Stata 13's "ralloc" randomization module and blinded study IDs provided by study staff. The decision support tool intervention will then be introduced in a short orientation to the providers randomized to the intervention arm.

B. Intervention Phase Procedures

Study staff role: UCSF Research Assistants will track all recruitment activity using the clinic-specific Recruitment Tracking Log daily. Weekly totals will be tallied each Friday afternoon. At each recruitment shift in each clinic, there should be one UCSF Research Assistant (RA) who conducts eligibility and consent processes, and, if possible, one volunteer or Patient Stakeholder Representative who assists the RA with completing tracking logs, the time study, and managing iPads and other study equipment. Time study data will be collected in this phase the same as in the pre-intervention phase: patient arrival time, tool start and end time (if applicable), visit start time with clinician, and visit end time.

The procedure for provider participants is as follows:

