Sensitivity analyses. [MD-5] Because informative missingness would violate the covariate-dependent missing at random (CDMAR) assumption of the standard multiple imputation procedure, we will conduct sensitivity analyses in which we multiply impute missing data under plausible informative missing data mechanisms – in particular, lower contraceptive continuation rates among participants with missing values of this outcome, in one or both arms. [DR-3] In addition, we will conduct sensitivity analyses controlling for any imbalanced pre-randomization characteristics (e.g., age and parity) that predict outcomes, using 5% changes in the coefficient for the intervention as the criterion for covariate inclusion in the adjusted model. To characterize the influence of individual providers, we will estimate best linear unbiased predictions of the provider effects, and also fit models with additional random provider-intervention interactions, to capture heterogeneity in the effects of the intervention. In all analyses, we will transform continuous outcomes as necessary to meet the normality assumption, model departures from linearity in the influence of continuous covariates, check for influential points, and identify potentially important interactions.

Heterogeneity of treatment effects. [HT-1] We will assess modification of the effect of assignment to the intervention by the following 5 pre-specified factors: age, race/ethnicity, language, parental education, and clinic. We will assess evidence for effect modification by adding the effect modifier and its interaction with the treatment assignment indicator to the primary analysis models specified above. To limit inflation of the type-I error rate, we will only estimate within-stratum treatment effects if the interaction is statistically significant at a Bonferroni-corrected $P = 0.01$, and will cautiously interpret findings. These analyses will use multiply imputed data and corresponding inference methods.

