Specific Aim 2: For this aim, we will be assessing the effect of the intervention on counseling at the cluster (i.e., provider) level. We will use Dedoose software to analyze the audio recordings using modified grounded theory, with the coding performed by [name], [name], and [name], with input from patient stakeholder representatives. This coding will focus on the presence or absence of shared decision making and patient engagement in the decision making process. In conducting this coding, we will use concepts drawn from observational measures of shared decision making, including the OPTION scale and the Four Habits Coding Scheme, as well as insight into the counseling process gained through our previous observational study, to identify our initial thematic structure. We will perform iterative coding, with discussions between coders, the PI, and patient stakeholders to clarify concepts and resolve ambiguities. We will then, again in collaboration with stakeholders, qualitatively explore the extent to which the providers altered their behaviors following implementation of the intervention using memo writing, and ultimately compiling these into results.

Specific Aim 3: In order to determine the effect of the intervention on the experience of providing family planning care at the level of both the clinic and the provider, we will perform both qualitative and quantitative analyses. Quantitative analyses, including comparing consultation time and total clinic visit time for patients in the intervention and control group, will use similar methods to those described in Aim 1. We will also compare scores on each sub-scale of the Maslach Burnout Inventory (emotional exhaustion, depersonalization, and personal accomplishment), controlling for baseline values, between providers randomized to the intervention and those randomized to the control group in both bivariate

Last updated November 22, 2016

and multivariate analyses, again controlling for clustering by clinic. In addition, we will conduct a sensitivity analysis controlling for any imbalanced pre-randomization characteristics (e.g., age) that predict outcomes, using changes in the coefficient for the intervention as the criterion for covariate inclusion in the adjusted model. Thematic analysis of interview and focus group transcripts and recordings will again be performed using Dedoose software, using an iterative and collaborative process of coding as described in Aim 2.

Additional Analyses

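### The SAP computes consultation time as visit start minus visit end, and one undefined visit-end stamp closes both Aim 3 time outcomes

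*SAP*

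**What the plan says.** Aim 3 has two quantitative time outcomes. Protocol section VII.A defines both and gives no formula. The SAP (Outcomes of Interest, Specific Aim 3) repeats the definitions and adds a derivation for each.

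- **Total Clinic Visit Time.** Definition: "Total amount of time a patient spends in a clinic for a family planning visit, from check-in to check-out". Derivation: "Time of visit end minus time of check-in (recorded in clinic tracking sheets".
- **Time Spent with Contraceptive Counseling Provider.** Definition: "Total amount of time spent with the provider that is providing contraceptive counseling". Derivation: "Time of visit start minus time of visit end (recorded in clinic tracking sheets". A site note adds that "this measurement will be different at PP Valencia because consultation time included time spent with RHS and clinician".

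Protocol section III.B (Intervention Phase Procedures) lists the time-study fields as "patient arrival time, tool start and end time (if applicable), visit start time with clinician, and visit end time".

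For the analysis, the SAP (Methods of Analysis, Specific Aim 3) says that "comparing consultation time and total clinic visit time for patients in the intervention and control group, will use similar methods to those described in Aim"; the reference is to the first aim. Those methods are mixed effects models with fixed effects for clinic and random effects for provider.

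**The concern.** A duration is the later time minus the earlier time. The SAP does this for total clinic visit time and does the reverse for consultation time. Taken literally, the two outcomes run in opposite directions, and a longer consultation gets a lower value.

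The second problem does not depend on the first. Total clinic visit time is defined up to check-out but computed up to *visit end*. The same stamp closes consultation time, which by definition ends when the provider encounter ends. Neither document says which event *visit end* records, so the formulas and definitions cannot both be right unless the two events coincide.

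These two outcomes are the plan's quantitative evidence on the time the tool costs clinics. What is at stake is the direction of one estimate and the interval to which one of the two results refers.

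**Working it through.** **Figure in the plan.** The only figure for these outcomes is in protocol section VII.B, Specific Aim 3: a detectable difference below 0.5 SD. As a rough check, assume all 758 patients are timed and use design effects from 1.0 to 1.7, as tabulated there for other outcomes. At 80% power and two-sided 5%, the detectable difference is (1.96 + 0.84) × √(4 × DE / 758), which is about 0.20 SD at DE = 1.0 and 0.27 SD at DE = 1.7. The statement is plausible on these assumptions and does not depend on sign, so nothing below disputes it.

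**Part 1: order of subtraction.**

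1. Let S be visit start and E visit end, with E later than S. The rule gives S − E = −(E − S), which is negative.
2. Let d be the mean of E − S in the intervention arm minus the mean in the control arm. For S − E the same contrast is −d. In a linear model, multiplying the outcome by −1 changes the sign of the coefficient and leaves its standard error and p-value as they were.
3. Numerical check on simulated data (300 patients, 150 per arm, skewed positive durations, ordinary least squares without clustering; all values assumed):

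| Outcome | Estimate (min) | SE | p |
|---|---|---|---|
| End minus start | +2.17 | 1.03 | 0.035 |
| Start minus end, as in the SAP | −2.17 | 1.03 | 0.035 |

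Only the direction changes.

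**Part 2: one stamp, two endpoints.** Set side by side:

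| Outcome | Defined end | End used in the formula |
|---|---|---|
| Total clinic visit time | Check-out | *Visit end* |
| Time with provider | End of time with the provider | *Visit end* |

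The protocol's field list has no check-out. Take assumed clock times: check-in 9:00, visit start 9:30, end of provider encounter 9:50, check-out 10:05. Subtract in the right order for both outcomes.

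| Meaning of *visit end* | Clinic time (definition gives 65 min) | Consultation time (definition gives 20 min) |
|---|---|---|
| End of encounter, 9:50 | 50 | 20 |
| Clinic departure, 10:05 | 65 | 35 |

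The 15 minutes between 9:50 and 10:05 fall on one outcome or the other. Both definitions are met only if that gap is zero. The documents do not give its length, so the real discrepancy cannot be computed. Under the SAP rule as written, consultation time in the first row would be 9:30 − 9:50 = −20 minutes.

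The site note on Planned Parenthood Valencia concerns whose time is counted. It does not settle the order of subtraction or the meaning of *visit end*. The start of clinic time is also labelled differently: *check-in* in the SAP formula and *patient arrival time* in the protocol's list.

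**The case against.** The strongest reply to Part 1 is that nobody would act on it. The definition directly above the formula shows that a positive duration is meant, the neighbouring formula is in the right order, and a variable that is negative for every patient is obvious at the first summary. Most of this stands. Two limits remain: the SAP's planned plausibility checks are worded for data needed for the primary analyses, so they do not formally cover Aim 3, and no other text corrects the rule.

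On Part 2, the reply is that *visit end* may mean the end of the clinic visit. The protocol ties the clinician to the start time only, and its labels are loose, as arrival and check-in show. That reading is open, but it moves the mismatch to consultation time and does not remove it. It is also fair that stopping the clock at the end of the encounter is defensible, because a research survey follows the visit (protocol III.B). The definition should then say so.

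A reader might infer four stronger things that the documents do not support.

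- *The trial will report longer counseling as shorter.* This requires the slip to be coded verbatim and to go unnoticed.
- *The planned transformation is impossible.* The SAP says only that "we will transform continuous outcomes as necessary to meet the normality assumption" and names no log; anyone who tried one would find the error at once.
- *Check-out was never recorded for anyone.* This rests on one list in the protocol. The SAP cites clinic tracking sheets, whose fields are not reproduced.
- *The tool's time cost is missed.* The tool is used in the waiting room before the visit, so its direct time cost lies inside arrival to visit end on either reading.

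**Conclusion.** The point holds, as a minor one. The derivation of consultation time is wrong as written: it yields negative durations and, if coded literally, an arm effect of the same size with the opposite sign. It is very probably a drafting slip. Separately, the formulas for the two time outcomes share an undefined stamp that cannot satisfy both definitions unless check-out and the end of the provider encounter coincide. No plausibility check would show this, because visit end minus check-in gives credible positive values whichever event was recorded.

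The sign result rests on a linear model for an untransformed outcome. The size of the Part 2 discrepancy is unknown. Neither part touches the primary outcome or the Aim 1 secondary outcomes.

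**What to change.** 1. In the SAP, Specific Aim 3, write time with the provider as visit end minus visit start.
2. Define *visit end* in the SAP and in protocol section III.B, and use one term for arrival or check-in.
3. If *visit end* is the end of the provider encounter, relabel total clinic visit time in protocol section VII.A and in the SAP as check-in (arrival) to end of provider visit, and limit the conclusion to that interval. Alternatively, use a check-out time if the tracking sheets hold one.
4. If *visit end* is clinic departure, keep total clinic visit time as it is and state that consultation time includes time after the encounter.

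The cost is wording in two documents, with no new data and no change to the models. The drawback is a slightly narrower claim about one of the two time outcomes.
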